Document: Protocol and SAP

Study title: Neuronal and Behavioral Effects of Implicit Priming in Obese Individuals

NCT: NCT02347527

Document date: 7/02/2015

COMIRB Protocol

COLORADO MULTIPLE INSTITUTIONAL REVIEW BOARD
[name] [contact] [contact]

Project Title (COMIRB): Effects of implicit priming on food cue responses

Principal Investigator: [name]

Co-Investigator: [name].

Version date: 7/02/15

I. Hypotheses and Specific Aims:

The development of novel strategies to promote weight loss and maintenance is critical, given the increasing prevalence of obesity in the United States. Greater responsiveness to high-calorie foods may lead to greater intake of these foods, contributing to obesity. The main aim of the current pilot project is to inform the development of a potential weight loss tool by assessing how priming pictures of food affects ratings. To achieve this goal, participants will be assigned to either the (a) active group or (b) control group. In the active group, images of high- and low-calorie foods will be paired with implicitly presented (below perceptual threshold) images of either negative or positive valence (high-calorie paired with negative; low-calorie with positive). For example, an ice cream image primed with an image of a pizza with cockroaches on it, or a piece of fruit primed with an image of a smiling child. During this task, participants will not perceive these primed pictures (although they will be told that they are there), and will rate each food picture on whether the food is "healthy" or "not healthy". Those in the control group will be primed with neutral images. Brain responses to food pictures will be recorded before and after the priming task. Participants will rate pictures of foods before and after the priming task on how much they "desire to eat" each food. In addition, participants will eat a buffet-style breakfast and lunch after the priming task, to see how the task affects food intake.

II. Background and Significance:

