The proposed study is the first step in a larger goal to identify a technique to promote healthier eating that would neuronal responses to food cues and food intake behaviors. This pilot study will investigate an implicit priming task, in which positive or negative images are presented immediately prior to food images, but are not consciously perceived. This pilot study will identify whether implicit priming can alter ratings of food pictures on “desire to eat.” In addition, we will assess how priming alters brain responses to food and food intake. The results of this study will inform the development of a larger study to implement this approach as an intervention to promote healthier eating habits.

Previous studies have found implicitly pairing target pictures with pictures or words of positive/negative valence (e.g., pairing a flower picture with the word “stench”) lead to increased liking/disliking of the target picture²³. These effects may be quite durable, as one study found alterations in ratings of target pictures to remain 2 months later²⁴. As such, this approach has the potential to reduce the appeal of hedonic foods and increase the appeal of healthier foods, which could encourage reduced intake of high-calorie foods in favor of low-calorie foods, promoting weight loss and weight loss maintenance.

III. Preliminary Studies/Progress Report:

As this is a pilot study, there are no preliminary data to report. If the aims of the project are achieved, the next step would be to use the results to inform development of an intervention to promote healthy eating. The subsequent study will also investigate the effects of this intervention on neuronal responses and subsequent food intake.

IV. Research Methods

A. Outcome Measure(s):

Primary outcomes in this study will be:

- 1) Ratings of food pictures on “desire to eat”
- 2) Brain responses to food pictures
- 3) Food intake

B. Description of Population to be Enrolled:

The study will include adult participants between ages 21-65. Participants older than 65 years of age will not be included to avoid potential effects of aging on food perceptions.

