determined through body composition measurements taken at baseline, using BodPod. Also during the initial baseline visit, participants will be asked to complete several food/eating-related questionnaires: Eating Attitudes Test (EAT-26), Disgust Scale -R, Three Factor Eating Questionnaire (TFEQ), Power of Food Scale (PFS), and Food Craving Inventory (FCQ). In addition, participants will complete two brief surveys, one in which they will rate food pictures on “desire to eat” and another in which they will categorize foods as “healthy” or “unhealthy.” After baseline measurements, participants will be randomly assigned to either the (a) active group or (b) control group in a 1:1 ratio. In the active group, images of high- and low-calorie foods will be paired with implicitly presented (below perceptual threshold; presented for 20 ms) images of either negative or positive valence (high-calorie paired with negative; low-calorie with positive). During this task, participants will not perceive these primed pictures (although they will be told that they are there), and will rate each food picture on whether the food is “healthy” or “not healthy.” Those in the control group will be primed with neutral images. The priming task will be completed during functional magnetic resonance imaging (fMRI), to assess brain responses during the task. Additionally, participants will view a series of food pictures during fMRI recording immediately before and after the priming task. Following the priming/categorization task, participants will again complete the food picture ratings outside the MRI. Following this, participants may stay for an additional 4 hours, across which they will consume a buffet-style lunch to measure food intake. Subjects will also complete visual analog scale (VAS) ratings on their subjective hunger, fullness, and prospective food consumption at baseline, prior to, and 30/60 minutes after each ad libitum meal. The entire session will take approximately 2-6 hours. Participants may also be asked to return 3-5 days later to complete the food picture ratings again, which will take approximately 10 minutes.

D. Description, Risks and Justification of Procedures and Data Collection Tools:

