Ad-Libitum Food Intake: Ad-libitum intake will be measured during a lunch meal served after the fMRI priming task. The purpose of this method will be to use weigh and measure methods to quantify food intake and macronutrient content of the diet directly. Specifically, a research dietitian will work with the subject to provide meals that replicate, to the extent practical/possible, usual meals consumed by the subject. Subjects will be asked to not consume any other food or beverages and to maintain usual activities. All meals will be prepared by the metabolic kitchen of the Anschutz Health and Wellness Center (AHWC) and will be offered with 30% more food than predicted requirements. Subjects will be instructed to eat what they want and that they can request more of any food. This design should neither restrict intake, nor encourage over consumption. Food intake and macronutrient composition will be determined by ‘weigh and measure’ methods by the dietary staff of the AHWC.

Body composition: Fat mass and fat-free body mass will be measured at baseline, prior to the fMRI study day, using BodPod at the AHWC. The BodPod system employs air displacement plethysmography to determine body composition, through calculating body volume and measuring body mass³³.

Demographic measures: Participants will be asked to report their age, ethnicity, and body mass index (see “Demographics Form” attachment). A potential risk is discomfort at disclosing this information. It will be made clear that participants can choose not to disclose any of this information if they are not comfortable doing so.

Eating-Related Questionnaires: TFEQ to measure food-related behaviors including restraint, disinhibition, and hunger²⁹; PFS to assess the drive to eat palatable foods in the absence of

energy need or “hedonic hunger”³⁰; FCQ to assess food-related cravings³¹; Disgust Scale-R to measure disgust; and EAT-26 to assess risk for eating disorders³².

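### The lunch that measures food intake is called a buffet in Sections I and IV.C but is built from each participant's usual meals in IV.D; varied menus can blunt this primary outcome, and can bias it only if tailoring follows allocation or priming.

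*Combined protocol and SAP*

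**What the plan says.** Section IV.A lists food intake as the third of three primary outcomes, without choosing a metric. The meal that measures it is described in three places.

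- Section I: "participants will eat a buffet-style breakfast and lunch after the priming task, to see how the task affects food intake".
- Section IV.C: participants may stay on after the scan, and "they will consume a buffet-style lunch to measure food intake".
- Section IV.D, Ad-Libitum Food Intake: "a research dietitian will work with the subject to provide meals that replicate, to the extent practical/possible, usual meals consumed by the subject". The same paragraph says that the meals "will be offered with 30% more food than predicted requirements", and adds: "Subjects will be instructed to eat what they want and that they can request more of any food".

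On timing, IV.D states: "Ad-libitum intake will be measured during a lunch meal served after the fMRI priming task". IV.C places randomisation after the baseline measurements. Section IV.F compares eating behaviour measures between arms by independent-samples t-tests and names no covariate. No ad libitum meal precedes the priming task; the one-day run-in diet in IV.D is a prescribed eucaloric diet.

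**The concern.** The expected behaviour is set out in Section II: priming might lower the appeal of hedonic foods and raise that of healthier ones, "which could encourage reduced intake of high-calorie foods in favor of low-calorie foods". The priming pushes the two food categories in opposite directions. A substitution of this kind can be seen only where both categories are on the table. A common buffet with set items ensures that; a lunch modelled on habit does not.

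There are two consequences. First, if the foods differ from person to person, part of the spread in intake reflects what was served, and the planned t-test has neither a baseline meal nor a covariate with which to remove it. Second, a participant whose usual lunch is nearly all of one category has little to switch to. A null result on this outcome could then mean either that priming did nothing or that the meal gave it no room to act. The pilot is meant to inform a larger study, so that ambiguity would carry forward.

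**Working it through.** **Comparing the sections**

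1. *Format.* Sections I and IV.C say buffet-style; IV.D says usual meals, planned person by person. A buffet made up of someone's usual foods is conceivable, so the wordings are not strictly exclusive. They are unreconciled, and under IV.D the foods offered differ between participants on either reading.
2. *Range of foods.* No section gives a menu, a number of high- and low-calorie items, or starting weights. The amount is tied to predicted requirements, so it also varies by person.
3. *Timing.* Only the serving of lunch is placed after priming, and hence after randomisation. When the dietitian plans the menu is not stated. It could be at the baseline visit, before allocation.
4. *Knowledge of arm.* Nothing says whether the dietitian or kitchen knows the allocation.

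**Illustrating the direction of the effect**

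The documents give no sample size, effect size, SD, alpha or power, so there is no stated figure to reproduce. All inputs here are assumptions: two-sided alpha 0.05, 1:1 allocation, within-menu SD 1, standardised effect d = 0.8, normal approximation.

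- Power = Φ(δ / (σ√(2/n)) − 1.96), with n per arm.
- n per arm for 80% power = 2(1.96 + 0.842)²σ²/δ².
- Extra variance v from individual menus: σ² = 1 + v, so n is multiplied by 1 + v.
- A share f of menus that allow no shift: δ = d(1 − f), so n is multiplied by 1/(1 − f)².

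| Scenario | Power at 20 per arm | Multiplier of n | n per arm for 80% power |
|---|---|---|---|
| Common menu (v = 0, f = 0) | 0.72 | 1 | 25 |
| v = 0.25 | 0.62 | 1.25 | 31 |
| v = 0.50 | 0.54 | 1.50 | 37 |
| v = 1.00 | 0.43 | 2.00 | 50 |
| f = 0.10 | 0.62 | 1/0.81 = 1.23 | 31 |
| f = 0.25 | 0.48 | 1/0.5625 = 1.78 | 44 |
| f = 0.50 | 0.24 | 1/0.25 = 4.00 | 99 |

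Worked line for v = 0.50: 0.8 / (√1.5 × √(2/20)) = 2.066; 2.066 − 1.96 = 0.106; Φ(0.106) = 0.54. With d = 0.5 the pattern is the same: power at 20 per arm is 0.35 for a common menu, 0.25 at v = 0.50 and 0.22 at f = 0.25.

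**Checking for bias**

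The t-test was simulated with no true priming effect (20,000 runs, 20 per arm, v = 0.5).

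- Menus independent of arm: type I error 0.047, mean difference about 0.
- Menus that shift intake in one arm by 0.2 within-menu SD: type I error 0.077.
- The same with 0.5 within-menu SD: type I error 0.241.

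Varied menus alone therefore cost power. They produce a false difference only when the tailoring depends on arm.

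**The case against.** Section IV.D does not confine people to a fixed plate. It offers more than predicted needs, lets subjects ask for more of any food, qualifies the replication as far as practical, and gives a rationale: the design should neither restrict intake nor push people to overeat. The study also excludes current dieters, vegans and vegetarians, which plausibly removes some lunches made up almost wholly of low-calorie foods. A common menu brings variance of its own through liking and familiarity, so v above is the net excess of individual menus over a common one, and the documents do not establish its size or sign. These points stand as limits on the magnitude. They do not supply a menu containing both categories: being able to ask for more of any food does not define a common range.

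The outcome metric is also open. The plan names food intake and measures macronutrient content; it does not define a high-calorie share. If total energy is meant, a person offered only high-calorie foods can still eat less, so the zero-shift assumption behind f would fail. Varied menus do not become harmless, however. The hypothesis then predicts less eating from a mostly high-calorie lunch and more from a mostly low-calorie one, and these can cancel in the mean.

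A reader might infer that the menu is tailored after randomisation and that the comparison of arms is therefore biased. The documents do not support this. They place only the serving of lunch after allocation and are silent on when, and by whom, the menu is planned. Menus fixed before randomisation, or by staff unaware of arm, balance in expectation.

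**Conclusion.** The inconsistency between the buffet wording and IV.D is real and affects a primary outcome. Followed as written, IV.D lets the foods on offer vary between participants and does not ensure that a shift from high- to low-calorie foods is possible. This can blunt the comparison whenever the menu is set.

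Bias between arms is a conditional risk: it needs tailoring that follows allocation or priming, and the documents neither say that this happens nor rule it out.

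The amount of blunting is unknown. The power figures show direction and plausible scale under assumed inputs; they are not estimates for this trial, and no multiple of its sample size should be quoted from them. The conclusion also assumes that the t-tests planned for eating behaviour measures are the intended test of lunch intake, since no other test of intake by arm is named. The change should be made, because it is cheap and matches the buffet format that the plan itself states.

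**What to change.** In IV.D, replace the sentence on replicating usual meals with one common buffet menu for the research meal: the same items and starting weights for everyone, a set number of high- and low-calorie items, and refills only from those items. Bring the statement on the amount offered into line with this. Agree and record any substitution for allergy or intolerance before randomisation, or have it set by staff unaware of arm. While editing, name the intake metric in IV.A, and settle whether the breakfast mentioned in Section I is part of the test, since IV.C and IV.D describe only a lunch.

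The cost is protocol wording and one standard kitchen menu, which should be simpler to run than individual menus. The small downside is that some participants will like fewer of the items. That adds some variance, but it is balanced between arms in expectation.

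If usual meals are kept, the least that is needed is to fix and record each menu before randomisation, or have it set by staff unaware of arm. That removes the route to bias but not the blunting.

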Priming/categorization task: In the active group, images of high- and low-calorie foods will be paired with implicitly presented (below perceptual threshold; presented for 20 ms) images of either negative or positive valence (high-calorie paired with negative; low-calorie with positive). For example, an ice cream image primed with an image of cockroaches on food, or a piece of fruit primed with an image of a smiling child. The negative and positive images used for priming were taken from the International Affective Picture System (IAPS; csea.phhp.ufl.edu), which is a large set of standardized color photographs ranging across a wide variety of categories. These pictures have been rated for emotional valence. We will exclude the most emotionally arousing negative pictures to avoid using images that could make participants overly uncomfortable, so will only use those with an arousal rating of less than 7. During the task, participants will not perceive these primed pictures (although they will be told that they are there), and will rate each food picture on whether the food is “healthy” or “not healthy,” as fast as possible. Those in the control group will be primed with neutral images and will also rate the food pictures as “healthy” or “not healthy.” The task will be performed during fMRI recording using Eprime 2.0, which will allow us to collect reaction time and response data for the response to each picture. The entire task takes approximately 10 minutes. As with the rating task, a potential risk of this procedure is fatigue. As with the rating task, this task is also only 10 minutes, so minimal risk of fatigue is anticipated. To mitigate this risk, participants are given short breaks between portions of the experiment. In the unlikely event of a computer malfunction, there is a very small potential risk that the screen may pause on one of the priming images (which are usually not perceived). If this were to happen on an image of negative valence, there is potential for the participant to be uncomfortable if it were an image they found to be unpleasant (e.g., cockroaches on food). The computer used to present the stimuli has been tested extensively to ascertain that it is fast and powerful enough to complete the paradigm with no pauses. In 30 test runs, the computer has not once paused during picture presentation. We have also used a high-speed video camera (with slow motion playback) to ascertain that the computer being used is presenting the priming stimuli for 20 ms, as desired. There are no known risks to the types of magnetic fields and radio waves that are used in functional MRI studies. However, some types of metal may be moved or may heat up by the magnets in the MR scanner. The MRI machine is a small round tube. Subjects with claustrophobia may feel uncomfortable. Very rarely, some people experience warmth and reddening of the skin. This usually goes away after a few minutes. As such, we feel that the risks are minimal.

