Response and reaction time data for the response to each picture during the priming task will be collected via the presentation software (Eprime 2.0). These data will be imported into SPSS version 21 (IBM Corp., Armonk, NY). Responses will be split into high- and low-calorie foods, which will be compared using paired-samples t-tests. The food ratings are performed using the ImageRate program ²⁸, which saves results in a spreadsheet. These ratings (for pre- and post-priming) will be imported into SPSS and split into high- and low-calorie foods. The change between session 1 and session 2 will be assessed for both high- and low-calorie foods using paired-samples t-tests. Group comparisons (control vs. active) will use independent-samples t-tests and the interaction between high- and low-calorie foods (difference in the change between each category) will also be tested.

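### The only test named for the priming-task responses compares food categories within person, so it cannot isolate a priming effect

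*Combined protocol and SAP*

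**What the plan says.** Section IV.F (Data Analysis Plan) opens with the data from the priming task: "Response and reaction time data for the response to each picture during the priming task will be collected via the presentation software (Eprime 2.0"). After import into SPSS, the stated analysis is: "Responses will be split into high- and low-calorie foods, which will be compared using paired-samples t-tests". The sentence names no arm and does not say whether the test is run within each arm or on both arms together. It speaks of responses only. That reaction times are handled the same way is an inference, though a natural one, because the preceding sentences introduce both kinds of data together.

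The same paragraph then turns to the desire-to-eat ratings, their change between sessions, and finally: "Group comparisons (control vs. active) will use independent-samples t-tests and the interaction between high- and low-calorie foods (difference in the change between each category").

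On the task itself, sections I, IV.C and IV.D fix the active-arm pairing as "high-calorie paired with negative; low-calorie with positive". Section IV.D says that active participants "will rate each food picture on whether the food is “healthy” or “not healthy,” as fast as possible", and for the other arm: "Those in the control group will be primed with neutral images and will also rate the food pictures as “healthy” or “not healthy". Section IV.C has participants "randomly assigned to either the (a) active group or (b) control group in a 1:1 ratio".

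Section IV.A lists three primary outcomes: "ratings of food pictures on “desire to eat", brain responses and food intake. Priming-task responses and reaction times are not on that list.

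**The concern.** In the active arm, prime valence and food category are the same variable: knowing one gives the other. A high- versus low-calorie contrast in that arm is the sum of two things. One is the difference in how foods of the two kinds are judged healthy, and how quickly, with no prime at all. The other is whatever the primes add. The judgement asked for is whether a food is healthy, so a sizeable category difference is to be expected without any priming.

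The randomized control arm does the same task with neutral primes, so it supplies the category difference alone. The stated test makes no use of that. A significant result would show that the categories differ and say nothing about priming. A null result in the active arm could hide a priming effect that cancels the category difference. The pilot is meant to inform a later intervention, and these are its behavioral measurements from the priming task itself, so it is worth analyzing them in a way that can speak to priming.

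**Working it through.** **No figure to reproduce.** The documents state no sample size, significance level, effect size or SD for this analysis. The aliasing follows from the design alone; the numbers below only illustrate its size.

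**Inputs from the documents.** Active arm: valence fixed by food category (IV.C, IV.D). Control arm: neutral primes, same judgement (IV.D). Allocation 1:1 (IV.C). Test: paired t, high versus low (IV.F).

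**Assumptions, not from the documents.** Two-sided 5% level; n = 10, 20 or 30 per arm; category difference c = 0.3, 0.5 or 0.8; priming effect p = 0 or 0.5 in size. Effects are in units of the SD of the within-person difference, taken as 1 in both arms.

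**Model.** Let D be a participant's low-minus-high difference.

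- Mean of D in the active arm: c + p
- Mean of D in the control arm: c
- Mean of D with arms pooled 1:1: c + p/2
- Active minus control: (c + p) − c = p

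The paired test asks whether the first, second or third of these is zero. Only the fourth isolates p.

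**Step 1: paired test with no priming (p = 0).** The statistic follows a noncentral t with N − 1 degrees of freedom and noncentrality c√N, where N is the number of participants tested. For c = 0.5 the noncentrality is 0.5√20 = 2.24, 0.5√40 = 3.16 and 0.5√60 = 3.87 at N = 20, 40 and 60. Rejection rates:

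| n per arm | c | One arm (N = n) | Both arms pooled (N = 2n) | Between-arm test on D |
|---|---|---|---|---|
| 10 | 0.3 | 13.6% | 24.7% | 5.0% |
| 20 | 0.3 | 24.7% | 45.7% | 5.0% |
| 30 | 0.3 | 35.5% | 62.8% | 5.0% |
| 10 | 0.5 | 29.3% | 56.5% | 5.0% |
| 20 | 0.5 | 56.5% | 86.9% | 5.0% |
| 30 | 0.5 | 75.4% | 96.8% | 5.0% |
| 10 | 0.8 | 61.6% | 92.4% | 5.0% |
| 20 | 0.8 | 92.4% | 99.9% | 5.0% |
| 30 | 0.8 | 98.8% | about 100% | 5.0% |

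With p = 0 the paired test rejects at 5% only if c is exactly zero. Simulation with 20,000 trials per scenario, run for c = 0.5 and 0.8, agreed.

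**Step 2: priming that opposes the category difference (c = 0.5, p = −0.5).** The active-arm mean is 0.5 − 0.5 = 0. The simulated active-arm paired test rejects in 4.7%, 5.1% and 4.7% of trials at n = 10, 20 and 30: a real priming effect is invisible to it.

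**Step 3: what the arm comparison delivers.** An independent-samples t-test on D has 2n − 2 degrees of freedom and noncentrality p√(n/2). For p = 0.5 this is 0.5√5 = 1.12, 0.5√10 = 1.58 and 0.5√15 = 1.94 at n = 10, 20 and 30, giving power of about 19%, 34% and 48%. These values do not depend on c.

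**The case against.** **The test may be only a check of categorization.** The plan never calls the paired test a test of priming and attaches no priming hypothesis to it. Confirming that participants sort the foods as expected is a legitimate use. This stands. A reader might infer that the plan will present a significant paired result as evidence that priming works; no text says so. What remains is that no test clearly named for these data can address priming.

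**The group-comparison sentence may already cover them.** Its first clause is not expressly limited to ratings, and the reference to change belongs to the second clause, on the interaction. This stands in part. But the sentence follows the rating analysis, its interaction is defined on a change over time, and the priming task is performed once. Even read broadly, it does not say that each person's category difference is to be compared between arms. The plan is unclear here, which is less than saying that it rules the comparison out.

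**A baseline exists.** Section IV.C includes a survey before randomization in which foods are sorted as healthy or unhealthy, so a prior measure of the response is available. IV.F does not mention using it, and no reaction times are described for it.

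**The control arm is used elsewhere.** A reader might infer that the trial wastes its randomized comparison. It does not: IV.F compares the arms on the ratings, on fMRI change and on eating-behavior measures.

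**The percentages rest on assumptions.** They are the power of a paired t-test to detect a genuine category difference, under assumed sizes and, in one column, pooling that the plan does not state. They are not false-positive rates for any claim the plan makes. The aliasing argument does not need them.

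**Conclusion.** The point holds at low severity. The test named for the priming-task responses, and by inference for the reaction times, can show that the food categories differ. It cannot show a priming effect, and it could mask one that runs the other way. That conclusion rests only on the fixed pairing of valence with category and on the absence of an arm term. The rejection rates depend on the assumed sample and effect sizes.

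It does not follow that the trial's main conclusions are affected. These are ancillary data, outside the three primary outcomes. Nor does a better test make the pilot informative about small priming effects: with 10 to 30 per arm, an effect of 0.5 SD would be detected less than half the time. The gain is that the analysis would answer the priming question at all, with an honest statement of precision.

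**What to change.** Add one line to section IV.F. For each participant, compute the low-minus-high difference in reaction time and in the proportion of pictures answered healthy. Compare each difference between active and control with an independent-samples t-test, and report the estimated difference between arms with its confidence interval. Given the power above, present it as an estimate and do not read a non-significant result as absence of priming.

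Keep the paired high- versus low-calorie test, labeled as a descriptive check that participants categorize the foods as expected. State that it covers reaction times as well as responses, if that is intended, and whether it is run by arm or pooled. Also say whether the existing group-comparison sentence is meant to apply to these data.

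The cost is a few words in the plan: same data, same software, no added participant burden.
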